6.2 Drug Therapy

6.2.1 Safety run-in dosing for enrolled subjects who have CD4 count $\leq 200/\text{mm}^3$ (0.2 x 10⁹/L)

The first three subjects who are enrolled who have a CD4 count $\leq 200 \text{ mm}^3$ (0.2 x 10⁹/L) (inclusive) will be prescribed a dose of 25mg/m² (Dose Level -2, refer to [Section 6.2.2](#)). This was the recommended MTD achieved in a prior African trial in HIV-infected women with LACC (21). Once the first three subjects with low CD4 count are enrolled, enrollment will be held for subjects with CD4 counts $\leq 200/\text{mm}^3$ until toxicity assessment is completed by the protocol team after the completion of treatment (or discontinuation from treatment) for all three subjects.

6.2.2 Definition of Dose-Limiting Toxicity for Cisplatin

Dose-limiting non-hematologic toxicities for cisplatin are defined as any grade 3 or worse peripheral neuropathy or ototoxicity OR any grade 4 GI toxicity that are at least possibly related to cisplatin. Dose-limiting hematologic toxicities for cisplatin are defined as any grade 4 anemia, thrombocytopenia, or neutropenia that are at least possibly related to cisplatin.

- 1) If no patient out of the initial three on this dose level exhibits a DLT, then escalate to dose level 0.
- 2) If one patient out of the initial three patients on a dose level exhibits a DLT, then up to three additional patients will be added. If a second patient develops a DLT, even if it is before there are six total patients on that level, then the MTD has been exceeded and no additional patients should be added to this or any higher doses. Thus, the MTD is defined as the highest dose level at which $\leq 1/6$ patients have a DLT. If ≥ 2 patients on a dose level experience a DLT, then the MTD will have been exceeded and no additional patients will be added at that dose level or any higher level.

If dose-limiting toxicity occurs at dose level -2, cisplatin will be discontinued for the remainder of the treatment with radiation therapy alone. The protocol team will review the toxicity and frequency of dose reductions of subjects enrolled in this safety run-in. If the protocol team determines that there is unacceptable toxicity and frequent dose reductions at the 40 mg/m^2 dose in enrolled subjects with a CD4 count $\leq 200/\text{mm}^3$ ($0.2 \times 10^9/\text{L}$), the protocol team will consider reducing the dose for all enrolled subjects with low CD4 counts to dose level -1 or dose level -2 for the remainder of the trial.

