6.2.3 Dose Modifications for Cisplatin

If different dose levels for cisplatin are required because of two different types of toxicities, use the dose level requiring the greatest reduction. There will be no dose re-escalation once the cisplatin is dose reduced.

The following levels should be used for cisplatin dose reductions:

Dose Level 0	Dose Level -1	Dose Level -2
40 mg/m^2	30 mg/m^2	25 mg/m^2

There will be no dose reduction below dose level -2 (i.e. cisplatin will be discontinued if further toxicity occurs).

Chemotherapy should not be administered during a radiation therapy delay.

All chemotherapy-related toxicities will also be graded according to the Common Toxicity Criteria (CTCAE v4.0).

Radiotherapy will not be omitted or delayed for chemotherapy-related toxicities unless the investigator considers that the participant is too sick to be treated.

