6.2.5 Nephrotoxicity

If serum creatinine is ≥ 1.5 mg/dL (133 μ mol/L) on the planned treatment date, estimate the creatinine clearance (CrCl) by the Cockcroft and Gault Equation for women:

$$\text{CrCl (mL/min)} = (140 - \text{age in years}) \times (\text{Weight in kg} \times 0.85) / (72 \times \text{serum creatinine})$$

Denominator for SI units (mL/s) = $(48816 \times \text{serum creatinine in } \mu\text{mol/L})$

Calculated Creatinine Clearance (CrCl)	Management
< 60 but ≥ 50 mL/min (<1.00 but ≥ 0.84 mL/s)	Hydrate as clinically indicated. Treatment with cisplatin may continue at a one level reduction in the cisplatin dose.
< 50 but ≥ 40 mL/min (< 0.84 but ≥ 0.67 mL/s)	Hold cisplatin for one week and hydrate as clinically indicated. If repeat CrCl ≥ 50 mL/min (0.84 mL/s) after one week, may resume with a one level reduction in the cisplatin dose. If CrCl does not recover to ≥ 50 mL/min (0.84 mL/s) within one week, permanently discontinue cisplatin.
< 40 mL/min (< 0.67 mL/s)	Permanently discontinue cisplatin.

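### The run-in's closed DLT list omits nephrotoxicity, so a woman who permanently loses cisplatin under the renal stop rules does not count against escalation from 25 to 40 mg/m²

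*Combined protocol and SAP*

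**What the plan says.** **Run-in.** Under section 6.2.1 the first three women with CD4 ≤ 200/mm³ receive 25 mg/m² weekly (dose level -2). Enrollment of further low-CD4 women is then held "until toxicity assessment is completed by the protocol team after the completion of treatment (or discontinuation from treatment) for all three subjects".

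**DLT definition and rules (6.2.2).** The non-hematologic items are "Dose-limiting non-hematologic toxicities for cisplatin are defined as any grade 3 or worse peripheral neuropathy or ototoxicity OR any grade 4 GI toxicity". The hematologic items are grade 4 anemia, thrombocytopenia and neutropenia. All must be at least possibly related to cisplatin. There is no renal item and no catch-all. Rule 1 reads: "If no patient out of the initial three on this dose level exhibits a DLT, then escalate to dose level 0". Level 0 is 40 mg/m² (6.2.3). Under rule 2, one DLT in three adds up to three women, a second DLT means the MTD is exceeded, and the MTD is the highest level with at most 1 DLT in 6.

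**Team review.** After the rules, 6.2.2 says the team will look at toxicity and at how often doses were reduced in the run-in. The action it then spells out concerns unacceptable toxicity at 40 mg/m². The Synopsis makes the dose for later low-CD4 women, 40 mg/m² or no cisplatin, depend on a review of the first three.

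**Renal rules (6.2.5).** If serum creatinine is at least 1.5 mg/dL "on the planned treatment date, estimate the creatinine clearance (CrCl) by the Cockcroft and Gault Equation for women". Clearance below 40 mL/min ends cisplatin permanently. At 40–49 the drug is held for a week; if clearance is not back to 50 "within one week, permanently discontinue cisplatin", and if it is, treatment "may resume with a one level reduction in the cisplatin dose". At 50–59, "Treatment with cisplatin may continue at a one level reduction in the cisplatin dose".

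**The concern.** The run-in exists to decide whether low-CD4 women can go from 25 to 40 mg/m². Its decision variable is the DLT count, and that count cannot register a toxicity for which this protocol permanently withdraws the drug. Nephrotoxicity is not remote here: 4.3.1.3 lists it among cisplatin's adverse effects, and 4.2.3.2 warns that tenofovir, discouraged but not prohibited, may worsen it. If renal stops were the only toxicity in the first three women, the written rule would read the run-in as clean. Later low-CD4 women would then get a dose 60% higher. The same gap affects the 1-in-6 definition of the MTD.

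**Working it through.** The plan states no operating characteristics for the run-in, so there is no figure to reproduce.

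**1. Stop rules against the DLT list**

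| Event | Action | Counted as DLT? |
|---|---|---|
| Ototoxicity grade ≥ 3 | Discontinue (6.2.5.3) | Yes, if at least possibly related |
| Creatinine ≥ 1.5, CrCl < 40 | Permanent stop (6.2.5) | No |
| Creatinine ≥ 1.5, CrCl 40–49, not ≥ 50 within one week | Permanent stop (6.2.5) | No |
| Creatinine ≥ 1.5, CrCl 40–49 with recovery | Resume one level lower | No |
| Creatinine ≥ 1.5, CrCl 50–59 | Continue one level lower | No |

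Rows 1 to 3 all end cisplatin, but only row 1 can enter the count.

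**2. Limiting case.** Suppose all three run-in women reach CrCl < 40 with creatinine ≥ 1.5 and have no listed event. The count is 0/3, and rule 1 directs 25 → 40 mg/m² (40/25 = 1.6). If permanent renal stops counted, it would be 3/3 and the MTD would be exceeded.

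**3. How large a creatinine rise reaches the < 40 row.** By the 6.2.5 formula, CrCl = K/creatinine with K = (140 − age) × kg × 0.85/72. Entry requires CrCl ≥ 60 (3.1.3). From entry clearance C, creatinine starts at K/C and must exceed K/40 and be at least 1.5. The fold rise is therefore max(C/40, 1.5C/K). Ages and weights below are illustrative.

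| Age, weight | K | From CrCl 60 | From CrCl 80 | CrCl when creatinine = 1.5 |
|---|---|---|---|---|
| 45, 55 kg | 61.7 | 1.50 | 2.00 | 41.1 |
| 45, 50 kg | 56.1 | 1.60 | 2.14 | 37.4 |
| 50, 50 kg | 53.1 | 1.69 | 2.26 | 35.4 |
| 55, 50 kg | 50.2 | 1.79 | 2.39 | 33.4 |

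When K < 60, clearance is already below 40 by the time creatinine reaches 1.5, so the first action in the table is a permanent stop. This shows what the rule requires, not how often it happens.

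**4. Illustrative probabilities.** The documents give no renal-stop rate. The nearest figure, 10% in 4.3.1.3, is for mild renal dysfunction under chronic therapy and serves here only as a high value. Assume an explicit-renal-stop rate r of 2%, 5% or 10% per woman, and an independent listed-DLT rate of 10%.

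- At least one renal stop in three, 1 − (1 − r)³: 0.059, 0.143, 0.271.
- No listed DLT in three: 0.9³ = 0.729.
- Rule 1 escalates despite a renal stop, the product: 0.043, 0.104, 0.198. As the listed rate runs from 0 to 20%, the ranges are 0.059–0.030, 0.143–0.073 and 0.271–0.139.
- Two or more renal stops in three, 3r²(1 − r) + r³: 0.001, 0.007, 0.028.

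As worded, the chance of 0/3 stays at 0.729 whatever r is.

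**The case against.** The strongest reply is that the count does not act alone. Low-CD4 enrollment stays closed until the team has assessed toxicity, 6.2.2 puts toxicity in general and dose reductions within that review, and the Synopsis bases the next dose on it. Three women reviewed one by one are unlikely to have a permanent renal stop overlooked. This stands as a reason why wrong escalation is less likely than the bare rule suggests. A reader might infer that the protocol has no safeguard, or that it would in practice escalate after renal stops; the documents support neither. But the review has no threshold, and rule 1 is imperative and not made conditional on it. Appendix V, in text for Phase I trials, says escalation follows the protocol's rules.

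A reader might also infer that every row of the renal table ends cisplatin at 25 mg/m², because 6.2.3 says "There will be no dose reduction below dose level -2 (i.e. cisplatin will be discontinued if further toxicity occurs", and so that every row should be a DLT. The documents do not settle this. The milder rows let treatment continue or resume, and for blood counts 6.2.4.1 resumes at the same level once reductions are exhausted. Counting those rows would also catch trivial changes. At age 45 and 76 kg, K = 85.2 and CrCl 60 means creatinine 1.42; a rise to 1.50, about 6%, gives CrCl 56.8.

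Two further objections hold in part. Stage IIIB includes hydronephrosis, so an obstructive creatinine rise could be attributed to cisplatin. And a single renal stop in three would, if counted, only expand the cohort; the two or more that would halt the dose level are rare at the assumed rates.

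**Conclusion.** The gap is real and follows from the text: a permanent cisplatin stop under the two explicit rules of 6.2.5 is not a DLT, so rule 1 as worded can direct a 60% dose increase when run-in women have lost the drug to nephrotoxicity. The conclusion covers what the rule directs. What happens in practice depends on a team judgment with no stated criterion. The consequence is bounded: 40 mg/m² is already the dose for CD4 > 200, 6.2.5 still protects each woman afterwards, and 6.2.2 allows a later dose cut. The 4%, 10% and 20% figures rest on assumed, independent rates, ignore any team override, and include cases with only one renal stop, so they should not be read as the chance of a wrong decision. The handling of milder renal changes at level -2 is ambiguous and forms no part of this conclusion.

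**What to change.** 1. Add to the 6.2.2 DLT definition: *permanent discontinuation of cisplatin under the explicit stop rules of 6.2.5 (CrCl < 40 mL/min, or 40–49 without recovery to ≥ 50 within one week), at least possibly related to cisplatin*. Count it in both the 0/3 and the ≤ 1/6 rules.
2. Reword rule 1 to: *escalate to dose level 0, subject to the protocol team's safety review*.
3. Do not count CrCl 50–59, or 40–49 with recovery.

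No visit or test is added, because creatinine clearance is already calculated weekly (5.2.1). The cost is a run-in somewhat more likely to expand or not to escalate. With the illustrative rates of working step 4, the combined DLT rate is p = 1 − 0.9(1 − r) = 0.118, 0.145 or 0.190, against 0.10 now.

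- Chance of 0/3, (1 − p)³: falls from 0.729 to 0.686, 0.625 or 0.531.
- Chance of expanding to six, 3p(1 − p)²: rises from 0.243 to 0.275, 0.318 or 0.374.
- Chance that 25 mg/m² passes with at most 1/6, (1 − p)³ + 3p(1 − p)⁵: falls from 0.906 to 0.875, 0.824 or 0.730.

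Since the Synopsis offers no cisplatin as the only alternative to 40 mg/m², a failed run-in has its own price for later women. That is a reason to keep the added DLT to explicit stops and to take care over attribution.

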6.2.3 Dose Modifications for Cisplatin

If different dose levels for cisplatin are required because of two different types of toxicities, use the dose level requiring the greatest reduction. There will be no dose re-escalation once the cisplatin is dose reduced.

The following levels should be used for cisplatin dose reductions:

Dose Level 0	Dose Level -1	Dose Level -2
40 mg/m^2	30 mg/m^2	25 mg/m^2

There will be no dose reduction below dose level -2 (i.e. cisplatin will be discontinued if further toxicity occurs).

Chemotherapy should not be administered during a radiation therapy delay.

All chemotherapy-related toxicities will also be graded according to the Common Toxicity Criteria (CTCAE v4.0).

Radiotherapy will not be omitted or delayed for chemotherapy-related toxicities unless the investigator considers that the participant is too sick to be treated.

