6.2.4 Cisplatin Modifications

6.2.4.1 Blood/Bone Marrow (Hematologic) Adverse Effects

Granulocyte, ANC or Platelet Counts

Based on counts within 2 days prior to each scheduled cisplatin dose, give the following:

ANC or granulocytes/μL		Platelets/μL	Cisplatin
$\geq 1,500$	and	$\geq 100,000$	No Dose Reduction
1,499-1,000	or	99,999-75,000	Reduce by one dose level*
< 1,000	or	< 75,000	Hold*

Treatment should resume as soon as recovery from toxicity allows. If treatment is delayed for >2 weeks, notify the Study Chair. External RT should continue while drug is withheld.

*If the maximum number of prior dose reductions of cisplatin have been made, treatment may be held for up to two weeks for blood count recovery. Treatment will resume at the same dose level as there are no more dose reductions allowed.

Nadir blood counts or febrile neutropenia

For nadir neutropenia in the absence of fever or with fever which is successfully treated by oral antibiotics, there will be no dose adjustment.

Hold cisplatin during febrile neutropenia. For febrile neutropenia (ANC $\leq 500/\text{mm}^3$ ($0.5 \times 10^9/\text{L}$) and temperature $\geq 100.5^\circ\text{F}$ or 38°C) requiring intravenous antibiotics, the dose of cisplatin should be reduced by 1 dose level for the next and subsequent doses of chemotherapy.

For Grade 4 nadir thrombocytopenia (platelets $\leq 10,000$ ($10.0 \times 10^9/\text{L}$)), the dose of cisplatin should be reduced by 1 dose level for the next dose and for all subsequent doses of chemotherapy.

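### For a woman at Dose Level -2, Sections 6.2.2, 6.2.3 and 6.2.4.1 give conflicting cisplatin instructions after a low blood count

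*Combined protocol and SAP*

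**What the plan says.** All references are to the combined protocol and SAP.

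- **Section 6.2.1 (run-in).** "The first three subjects who are enrolled who have a CD4 count" of 200/mm³ or below "will be prescribed a dose of 25mg/m² (Dose Level -2, refer to" a later section). These women start at the lowest level.
- **Section 6.2.2 (dose-limiting toxicity, DLT).** "Dose-limiting hematologic toxicities for cisplatin are defined as any grade 4 anemia, thrombocytopenia, or neutropenia that are at least possibly related to cisplatin". The consequence at the lowest level is: "If dose-limiting toxicity occurs at dose level -2, cisplatin will be discontinued for the remainder of the treatment with radiation therapy alone". After one DLT among the first three women, up to three more may be added.
- **Section 6.2.3 (dose levels).** The levels are 40, 30 and 25 mg/m². "There will be no dose reduction below dose level -2 (i.e. cisplatin will be discontinued if further toxicity occurs".
- **Section 6.2.4.1 (pre-dose counts).** ANC 1,000-1,499 or platelets 75,000-99,999 calls for a one-level reduction. ANC below 1,000 or platelets below 75,000 calls for a hold. Beneath the table: "Treatment should resume as soon as recovery from toxicity allows". An asterisk on both rows leads to the footnote, which reads in part: "If the maximum number of prior dose reductions of cisplatin have been made, treatment may be held for up to two weeks for blood count". Its second sentence is: "Treatment will resume at the same dose level as there are no more dose reductions allowed".
- **Section 6.2.4.1 (nadir counts).** Nadir neutropenia without fever brings no dose adjustment. Grade 4 nadir thrombocytopenia, given there as platelets of 10,000 or below, brings a one-level reduction.

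**The concern.** Once a woman is at 25 mg/m², a low count is met by one section that ends cisplatin and another that pauses and resumes it. Two sites following the protocol in good faith could act in opposite ways on the same laboratory result.

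Three things are at stake. The first is safety: after a DLT, one passage stops the drug and another lets it continue. The second is the run-in, whose purpose is to see how low-CD4 women tolerate cisplatin; how much drug they receive after a low count would depend on which passage was followed. The third is the outcome data. Section 9.1.4 tracks dose delays, reductions and missed doses, and Section 11.2 makes treatment completion the primary outcome. All of these can move with the reading chosen.

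**Working it through.** No planning figure in the documents bears on this point, so the check is a comparison of the passages for a woman at Dose Level -2.

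| Situation at Dose Level -2 | 6.2.2 | 6.2.3 | 6.2.4.1 |
|---|---|---|---|
| Reduction band, woman reduced to -2 | silent (not Grade 4) | discontinue | may hold up to two weeks, resume at same level |
| Reduction band, woman who started at -2 | silent (not Grade 4) | discontinue | reduce one level, but none exists; footnote not literally met |
| Hold band, woman reduced to -2 | silent unless a DLT | discontinue | hold up to two weeks, resume at same level |
| Hold band, woman who started at -2 | silent unless a DLT | discontinue | hold, resume on recovery |
| Grade 4 neutropenia at afebrile nadir, a DLT | discontinue | discontinue | no dose adjustment |
| Grade 4 thrombocytopenia at nadir, a DLT | discontinue | discontinue | reduce one level, but none exists |

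**Women reduced to -2.** A woman starting at 40 mg/m² reaches 25 mg/m² after two reductions (40 to 30 to 25). She has had the maximum number of prior reductions, so the footnote applies to her on its own terms and contradicts Section 6.2.3 directly.

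**Women who start at -2.** They have had no reductions, so the footnote's condition is not met as worded. In the reduction band this leaves a gap in Section 6.2.4.1, with only Section 6.2.3 giving an outcome. In the hold band the general sentence on resuming after recovery still applies and still contradicts Section 6.2.3.

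**After a DLT.** Section 6.2.2 enters only for events meeting its definition, which for blood counts means Grade 4 and at least possibly related to cisplatin. The hold row has no lower limit, so it also takes in Grade 4 neutropenia and thrombocytopenia found before a dose. Grade 4 anemia is a DLT too, but Section 6.2.4.1 has no anemia row, so no clash arises there.

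**Link to completion.** Section 9.1.1 counts women who complete the cisplatin/RT regimen and Section 11.1 counts women who complete cisplatin. Neither gives a minimum number of cycles. Suppose all six are required:

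- A two-week hold moves cycle 6 from day 36 to 36 + 14 = day 50, inside the 56-day radiotherapy limit.
- If the hold begins at or before cycle 5, cycle 5 moves from day 29 to 29 + 14 = day 43. Whole-pelvis treatment ends at about day 35 (Section 4.6.8), and Section 6.2.6 provides only for the sixth cycle during brachytherapy. Unless a parametrial boost is still running, two cycles would fall in that period.

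A held woman may therefore still receive six cycles, though this is not assured. A woman discontinued before her sixth cycle cannot.

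**Reach.** If the run-in fills, 3 women start at -2, or up to 6 after one DLT: 3/38 = 7.9% and 6/38 = 15.8% of the 38 evaluable. This is a ceiling on run-in women who could meet the conflict, not a count of those who will. Women reduced to -2 are additional, and Section 6.2.2 also lets the protocol team consider moving all low-CD4 women to -1 or -2.

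**The case against.** The best defence is that the specific rule governs the general one. Section 6.2.3 would be the default where no lower level exists, and the blood-count section would override it. The structure lends this some support: the neurotoxicity section states its own rule at Dose Level -2, while the nephrotoxicity section and the section on other Grade 3/4 toxicity ask for one-level reductions without a floor rule, so Section 6.2.3 still has work to do. But no precedence is stated. The footnote does not literally reach women who started at -2, and the reading leaves the conflict with Section 6.2.2 after a DLT untouched.

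It could also be said that a mildly low count is not further toxicity. Section 6.2.4.1 itself speaks of recovery from toxicity directly beneath the count table, so that defence is weak.

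A third objection concerns the run-in. Escalation turns on DLTs, and a count in the reduction band is not a DLT under either reading. Nor is a hold or a discontinuation a dose reduction, the frequency of which the team reviews. This stands as far as it goes. The remaining route is indirect: stopping early shortens exposure and the opportunity to observe a DLT.

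**Conclusion.** The conflict is real, and it is a safety matter after a DLT. Women reduced to -2 face a direct contradiction. Women who started there face a gap in the reduction band and a contradiction in the hold band. Both groups face conflicting text after Grade 4 neutropenia or thrombocytopenia at least possibly related to cisplatin.

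Four stronger readings are tempting but not supported:

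- **Section 6.2.2 stops cisplatin for any further toxicity.** It does so only for a DLT; the broader wording belongs to Section 6.2.3.
- **Every run-in woman is caught between the footnote and Section 6.2.3.** The footnote requires prior reductions, and she has had none.
- **The same count necessarily makes a woman a completer or a non-completer.** Completion has no cycle threshold, and even a six-cycle rule leaves a held woman's status dependent on timing and Section 6.2.6.
- **The 3 to 6 women, or a probability, measure the effect.** Assuming that 30% to 50% of low-CD4 women have a qualifying count would give 1 - 0.7³ = 66% to 1 - 0.5³ = 88% for at least one of the first three. The documents give no such rate.

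The size of the effect therefore cannot be derived. If completion means six cycles, each evaluable woman whose status changes moves the observed proportion by 1/38 = 2.6 percentage points.

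**What to change.** Reconcile Sections 6.2.2, 6.2.3 and 6.2.4.1 (table, footnote and nadir paragraphs) into one instruction for women at Dose Level -2. It should cover separately:

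- counts in the one-level-reduction band;
- counts in the hold band;
- a DLT, including Grade 4 neutropenia and thrombocytopenia at nadir.

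State that it applies equally to women who started at -2 and to those reduced to it, so that the condition on prior reductions no longer separates them. Which instruction stands is for the sponsor to decide. The cost is amendment wording only, with no added participants or procedures.
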